- Within-host variation in influenza strains between the first and the third viral swab
- Cost effectiveness, assessed using health resource utilization (visit to clinic, hospital, pharmacy, emergency department) and school and work absenteeism
- Proportion with antiviral resistance, assessed by genetic sequencing of influenza strains from the drug eligible and drug ineligible study participants

Hypothesis

Primary hypothesis:

- A home-based approach to influenza infection control will result in a large percentage of drug eligible individuals diagnosed with influenza initiating antiviral therapy within 48 hours of symptom onset.

Secondary hypotheses:

- Home-based approach to influenza infection control and rapid delivery of antiviral therapy will decrease symptom severity in the drug eligible individuals diagnosed with influenza that administer antiviral therapy within 48 hours of symptom onset compared to drug eligible, influenza-infected individuals that administer antiviral therapy greater than 48 hours after symptom onset.
- Home-based approach to influenza infection control and rapid delivery of antiviral therapy will decrease the duration of viral RNA detection in the drug eligible, influenza-infected individuals that administer antiviral therapy within 48 hours of symptom onset compared to drug eligible, influenza-infected individuals that administer antiviral therapy greater than 48 hours after symptom onset.

IV. Study Population

The study will be conducted in households with at least 3 members, where at least 2 of these members must be eligible to receive BXM, in the Seattle area. Participants aged 12 years or older, weighing at least 40 kg, will be drug eligible. Participants of any age that reside in the same household as the case at least 4 days per calendar week will be drug ineligible study participants. Drug eligible study participants will receive baloxavir intervention when appropriate,

and all drug eligible and drug ineligible participants will receive a 7-day follow-up from the study team per illness episode.

Study size

The study is being conducted in the Seattle, WA area over one influenza season. The goal is to enroll 250 households, with enrollment occurring prior to and during the annual influenza season.

Household enrollment criteria

The household must meet all the following enrollment criteria:

Household inclusion criteria

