All sick individuals, meaning those drug eligible and those drug ineligible, will complete an illness questionnaire in REDCap 7 days after they report the illness. This questionnaire will collect information on the presence or absence of respiratory and systemic symptoms during the 7 days after reporting the illness. Data will also be collected on childcare, school, and work absenteeism, and subsequent visits to health care providers. Additionally, the influenza-diagnosed individual will provide nasal swab specimens collected via self-swab or parent/legal guardian-swab at Study day 2-3 and Study day 5-7. These swabs will be returned to the laboratory via a delivery services the day of or the day after collection (See VI. Laboratory Procedures section). In addition to the illness questionnaire, the drug eligible, influenza infected participant will complete a standard questionnaire at 7 and 14 days following study drug receipt to monitor for the occurrence of adverse events (AEs) or serious adverse events (SAEs). These questionnaires will be monitored by a member of the study team. Additionally, any provider consultations with tele-health following drug administration will be reported to the study team to monitor for the occurrence of adverse events (AEs) or (SAEs). Any reported adverse events will be assessed to determine if related to drug treatment and whether unexpected or not and subsequently reported to the IRB using a standardized AE and SAE form. After the self-collected nasal swabs have been tested in the laboratory, the case will have to ability to view the results of their swab on the Seattle Flu Study website.

For all individuals that provide nasal swab specimens for testing and further characterization, they will have the ability to view whether influenza or respiratory syncytial virus (RSV) was detected from their swab(s) on the Seattle Flu Study website (See VI. Laboratory Procedures).

Data collection

Data will be collected electronically in REDCap online via a computer or mobile device or through a text-message accessible app. The major data collection activities will occur at the following times (See Table 1).

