Data Items	Enrollment	Weekly during Influenza Season	Monthly during Influenza Season	Influenza not diagnosed, drug eligible group	Influenza diagnosed, drug eligible group	Sick, drug ineligible group
Informed consent	X					
Baseline health and demographic data collected	X					
Baseline nasal swab collection	X					
Self-monitor cough or 2 or more respiratory symptoms		X				
Report changes in household structure or influenza vaccine status			X			
Nasal swab collection (Study day 0)				X	X	X
Nasal swab collection (Study day 2-3)					X	
Nasal swab collection (Study day 5-7)					X	
Illness questionnaire (Study day 0, Study day 7)				X	X	X

Record timing of drug receipt					X	
Standard questionnaire for AEs and SEAs (48 hours , 7 & 14 days post-treatment)					X	

Medication management

Baloxavir (BXM)

Drug eligible, influenza-infected study participants will receive a one-time oral dose of baloxavir (Xofluza) based on weight. For individuals weighing 80kg or more, they will receive 80mg of BXM. For individuals weighing 40-80kg, they will receive 40mg of BXM (See Table 2). The drug will be delivered to the individual's home within 2-6 hours of an influenza diagnosis. The case will be instructed to take the medication immediately on receipt and record the time of ingestion using the REDCap app or by text message. The description of the antiviral from the product monograph is as follows:

XOFLUZA™ is a polymerase acidic (PA) endonuclease inhibitor indicated for the treatment of acute uncomplicated influenza in patients 12 years of age and older who have been symptomatic for no more than 48 hours.

Limitations of Use: Influenza viruses change over time, and factors such as the virus type or subtype, emergence of resistance, or changes in viral virulence could diminish the clinical benefit of antiviral drugs. Consider available information on drug susceptibility patterns for circulating influenza virus strains when deciding whether to use XOFLUZA.

Medication storage and packing

BXM blister packs will be provided to the study team prior to the start of the influenza season by the drug manufacturer or purchased from the manufacturer. According to the manufacturer, baloxavir should be stored in its blister package at 20°C to 25°C (68°F to 77°F); excursions permitted to 15°C to 30°C (59°F to 86°F). Additional storage recommendations are provided below.

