Serious Adverse Events: Serious adverse events (SAEs) under Good Clinical Practice (GCP) guidelines include death, a life-threatening reaction to the study drug (or placebo) or other study procedure, hospitalization, or significant or persistent disability or impairment. Other events may also be considered a serious adverse event if, based on medical judgement, the event jeopardized the patient to the point of requiring medical or surgical intervention to

Other Adverse Events: This will include any untoward medical event that occurs in a participant, any unfavorable sign or symptom temporally associated with the provision of the intervention, or any noxious or unintended response to the study drug. These other adverse events can be anticipated based on what we know about reactions to antiviral medications, or unanticipated. Examples of anticipated adverse events include (but are not limited to) instances of nausea, headache, or diarrhea.

Unanticipated adverse events are those that are either unexpected in terms of nature, severity, and frequency especially if they indicate that there is greater risk of harm than previously recognized.

Within 48 hours of taking the study drug, cases will be screened via REDCap for evidence of short-term reaction. Additionally, drug eligible, influenza-positive study participants will be

monitored at 7 and 14 days after receipt of the intervention using a standardized questionnaire. Any potential AE or SAE based on post-drug tele-health consultation will be reported to the study team as soon as possible, which will be entered into the standardized questionnaire. These questionnaires will be monitored by the data management team, such that adverse events will be reported as soon as possible. All SAEs (regardless of causality), and any grade 3 and 4 AEs which are deemed related or possibly related to the study drug, will be logged in AE database and reported using an official Adverse Event Report Form to the designated principal investigator ([name]) for review within 48 hours. This review will determine if there is any indication for the event being related to the study intervention or procedures. The medical expert team will review the file and make a determination regarding attribution to study procedures or the intervention.

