Person-to-person transmission: We will use the CDC definition for influenza transmission that refers to the ability of an influenza virus to spread from one person to another, most commonly through large or small droplets containing influenza virus that are expelled when a sick person is coughing or sneezing.

XI. Statistical Analyses

The primary objective is to precisely estimate the proportion of drug eligible individuals with an influenza diagnosis who initiate treatment within 48 hours. We define precision in terms of the width of a 95% confidence interval. The width of a 95% CI will be less than or equal to $\pm 1.96 \cdot 0.5/\sqrt{n}$ where n is the number of individuals who test positive for flu. With 250 households participating and an attack rate of 25% we expect 63 individuals with confirmed influenza infection. This will give a 95% CI for the proportion initiating treatment of ± 0.12 or less.

The proportion of drug eligible individuals receiving the drug and initiating treatment within 48 hours of symptom onset using home-based self-test and delivery methods will be estimated. Binomial regression with log link will be used to calculate the relative risk of receiving and initiating treatment within 48 hours by demographic and clinical factors, including age, sex, race/ethnicity, symptom types, symptom severity, and duration of symptoms. The RR, 95% confidence intervals and p-values will be reported.

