A list of serious adverse events will be presented by shelter and by treatment v. intervention period. As defined in the study protocol, serious adverse events include death, a life-threatening reaction to the study drug (or placebo) or other study procedure, hospitalization, or significant or persistent disability or impairment. The incidence of SAE's (events/person-days of follow-up) will be presented both (1) overall and (2) by case v. non-cases. We will test for a difference in SAE rate between the two study periods (intervention v. control) using an exact Poisson test in R.

Baloxavir-resistant influenza transmission

Evidence of a strong intervention effect causing incidence of baloxavir-resistant influenza strains will be evaluated using linear mixed effects logistic regression. The unit of analysis will be influenza-positive tests, and the outcome will be binary: baloxavir-resistant or not baloxavir-resistant.

B5. Power sample size

Table 1. Sample size calculations: Number of clusters needed per arm for two-group cluster-randomized trial - Household intervention study

Effect size (% reduction in flu incidence)			
Power	0.30	0.40	0.50
0.80	57	84	129
0.90	76	112	172

All calculations above assume an ICC of 0.29, anticipated average (or actual) cluster size of 4, and a 15% transmission rate for flu.

Based on these calculations, an arm size of 250 households should be sufficient to detect a 30% reduction in flu incidence at 90% power.

B6. Endpoint Analyses

Primary Analysis

[figure not shown]
Question: Does this home-based self-test diagnostic tool and rapid treatment intervention lead to a large percentage of influenza-positive individuals initiating antiviral therapy within 48 hours of symptom onset?

Endpoint: Cumulative incidence of influenza virus infection

Measure of Association:
Cumulative Incidence (Attack Rate, Incidence Proportion)

$$\text{Cumulative Incidence} = \frac{\text{Number of participants that successfully initiate antiviral therapy within 48 hours of symptom onset (among participants who have a cough and self-test positive for influenza) during the October 2019-May 2020 influenza season}}{\text{Number of influenza-free participants at risk at } t_0 \text{ (baseline)}}$$

Relevant DAG

Exposure:

Exposed (Treatment) = Participants who develop cough and self-test positive
Unexposed (No treatment) = Participants who develop cough but self-test negative

Outcome:

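### SAP B4 plans SAE rates per person-day overall and for cases against non-cases, but the AE/SAE form goes only to baloxavir recipients, to day 14; the overall rate would be understated and the contrast confounded by unequal ascertainment

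*SAP*

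**What the plan says.** SAP B4 (Safety Analysis, serious adverse events) gives the planned rate: "The incidence of SAE's (events/person-days of follow-up) will be presented both (1) overall and (2) by case v. non-cases". It does not say whose person-days count, when they start and stop, or what makes someone a case. SAP B1 does not settle this: one sentence describes the Primary Dataset both as everyone who enrols and as symptomatic drug-eligible people.

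On collection, Protocol V (Follow-up) says "the drug eligible, influenza infected participant will complete a standard questionnaire at 7 and 14 days following study drug receipt", and adds a screen at 48 hours. Table 1 of the protocol has one row for this form. Its single mark falls, by position in the extracted text, under the drug-eligible group diagnosed with influenza, which agrees with the prose. Protocol IX repeats the schedule.

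Protocol IX also sets a reporting rule, which covers "All SAEs (regardless of causality), and any grade 3 and 4 AEs which are deemed related or possibly related to the study drug". That rule says what is done with an SAE once it is known. It does not say how one would be found in a person who never took the drug.

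For every ill participant, treated or not, the day-7 illness questionnaire applies: "Data will also be collected on childcare, school, and work absenteeism, and subsequent visits to health care providers".

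**The concern.** A rate per person-day can be interpreted only if events are sought throughout the time in the denominator. Here they are sought in one small group for two weeks. Of the other scheduled contacts, the protocol's weekly log asks about cough and respiratory symptoms, and the monthly form about household structure and vaccination. If enrolled person-time is the denominator, most of it carries no SAE question.

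Two misreadings could follow.

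- **Overall rate.** It would look reassuringly low whatever happened among recipients. SAP section B intends these analyses for DSMB meetings as well as the final report.
- **Cases against non-cases.** With equal true SAE rates, the group that gets the form will show more events. The groups also do not line up with treatment. Protocol II allows only one baloxavir recipient per household, so secondary cases and drug-ineligible cases may count as cases without ever getting the form.

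This is separate from B4's test between study periods.

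**Working it through.** **The plan's own figure.** Protocol XI says: "With 250 households participating and an attack rate of 25% we expect 63 individuals with confirmed influenza infection". 250 × 0.25 = 62.5, rounded to 63. The stated precision also reproduces: 1.96 × 0.5/√63 = 0.123, given as 0.12. The documents give no SAE rate or person-time, so the rest is scenario arithmetic.

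**Inputs**
- Season 1 November 2019 to 1 May 2020: 182 days.
- 250 households of mean size 3, 4 or 5 (the documents' own scenarios).
- 63 recipients. This is an assumption: treatment follows a telehealth clinical diagnosis, so the number could be lower or higher.
- 14 solicited days per recipient.

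**Solicited time.** 63 × 14 = 882 person-days.

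**Enrolled time, full season.** 250 × size × 182 = 136,500, 182,000 or 227,500 person-days.

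**Understatement with no outside capture** (enrolled ÷ solicited, equal true SAE rates throughout)

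| Scenario | Size 3 | Size 4 | Size 5 |
|---|---|---|---|
| 63 recipients, 182 days | 155 | 206 | 258 |
| 63 recipients, 91 days (in-season enrolment) | 77 | 103 | 129 |
| 50 recipients (20% attack rate), 182 days | 195 | 260 | 325 |
| 25 recipients (10% attack rate), 182 days | 390 | 520 | 650 |

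**With some outside capture.** At size 4 and 63 recipients, let c be the fraction of SAEs outside the window that still reach the study. The factor is 182,000 / [882 + c × (182,000 − 882)].
- c = 5%: 182,000 / 9,938 = 18.3
- c = 10%: 182,000 / 18,994 = 9.6
- c = 25%: 3.9
- c = 50%: 2.0

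**If the day-7 questionnaire captured every SAE in its week.** With one illness in each of the 1,000 − 63 = 937 non-recipients, covered time is 882 + 937 × 7 = 7,441 person-days, a factor of about 24. With two illnesses each it is 882 + 2 × 937 × 7 = 14,000, a factor of 13.

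**If only recipients' time is counted, over the full season.** 63 × 182 = 11,466; 11,466 / 882 = 13.

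**Case against non-case, equal true rates.** If s is the solicited share of case person-time, the spurious rate ratio is 1 + s(1 − c)/c.
- Case means recipient: s = 14/182 = 0.077. The ratio is 2.5 at c = 5% and 1.7 at c = 10%.
- Secondary cases also count (34–72 at size 4 in the 25% scenario): case time is 97 × 182 = 17,654 to 135 × 182 = 24,570, so s = 0.050 to 0.036. The ratio is 1.9 to 1.7 at c = 5%, and 1.4 to 1.3 at c = 10%.

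**What zero events would look like.** The exact 95% upper limit on the count is 3.69. That is 3.69/882 = 4.2 per 1,000 solicited person-days, but 3.69/182,000 = 0.020 per 1,000 enrolled person-days. As a proportion, 0/63 has an upper limit of 1 − 0.025^(1/63) = 5.7%.

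**The case against.** The strongest reply is that B4 leaves terms undefined and that the large factors come from a denominator it never states.

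- **Denominator.** B4 does not say all enrolled person-days. Protocol IV speaks of a 7-day follow-up per illness episode, and SAP B1 can be read as symptomatic drug-eligible people only. Assuming 250 to 1,000 episodes of 7 days, the denominator is 1,750 to 7,000 person-days, only about 2 to 8 times 882. This stands: enrolled time is one possible reading, not the stated method.
- **Capture outside the window.** A reader might infer that SAEs in non-recipients cannot be recorded, so that non-cases show none by construction. The documents do not support that. All SAEs are reportable, the day-7 questionnaire asks ill participants about health-care visits, Protocol III makes hospital and emergency visits study data, and SAP B3 (Table 1b) takes care-seeking from the weekly diary. Hospitalization is itself an SAE criterion. What does not stand is that these routes equal solicitation: the questionnaire covers a week per illness, and none of them is described as an SAE form.
- **Nature of the contrast.** A reader might also call any case excess a pure artefact. That goes too far. It would be confounded by unequal ascertainment of unknown size. If secondary cases count, the numerical distortion shrinks, but the contrast then tracks neither treatment nor solicitation and is harder to interpret.
- **Consequence.** The rates are descriptive, B4 also lists individual SAEs, event-level review under Protocol IX does not depend on them, and no stopping rule is tied to them. This limits the harm but does not make the rates interpretable.

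**Conclusion.** The point holds in this form. SAE solicitation is confined to baloxavir recipients for 14 days. B4 plans a rate over undefined person-days, and a contrast between groups with different ascertainment. An overall rate on enrolled time would be understated, and the case contrast would be confounded.

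No single factor should be quoted as the plan's error. The 155- to 258-fold figures need 63 recipients, full-season follow-up of everyone and no outside capture. Other follow-up and attack-rate scenarios run from 77 to 650. Modest capture (5–10%) brings the factor to about 10 to 18 at size 4. A recipients-only, full-season denominator gives 13. The direction is the same in all of these, and the understatement disappears only if the denominator is matched to the time in which SAEs were sought.

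**What to change.** Rewrite the SAE paragraph of SAP B4:

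1. Define the safety set as everyone who took baloxavir.
2. Report participants with an SAE as n/N with an exact 95% CI.
3. Report a rate whose person-time runs from ingestion to the last AE questionnaire returned, at most day 14.
4. Drop the overall and the case against non-case SAE rates.
5. List separately, with no rate comparison, any SAE reported in non-recipients, including those related to study procedures such as swabbing.
6. If a between-group comparison is wanted, limit it to health-care use from the day-7 illness questionnaire. First reconcile its timing: Protocol V (Follow-up) sets it seven days after the illness is reported, while Protocol V (Data collection) sets it seven days after antiviral treatment for treated participants. Until then the windows cannot be treated as the same.

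The cost is SAP wording, plus reconciling the questionnaire timing if item 6 is used; no new data are needed. The reported SAE rate will be higher and its interval wider, and there will be no rate for non-recipients, whose SAEs appear only in the listing.

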[figure not shown]
II. Study design

This is a pilot study that will evaluate the feasibility of a home-based approach to influenza infection for households in the Seattle, WA area, utilizing an influenza self-test, followed by telehealth consultation for diagnosis and rapid home delivery of antivirals. Households with 3 or more of the same members at least 4 days per calendar week will be eligible to enroll, as long as there are at least 2 members in household eligible to take BXM. Individuals 12 years or older, weighing at least 40 kg, will eligible to take BXM, and thus, are able to enroll as drug eligible participants. Individuals that are not able to take BXM will be able to enroll in the study as drug ineligible participants. Individuals within an eligible household will be enrolled prior to or during the annual influenza season and monitored throughout the influenza season for the development of a cough or 2 or more respiratory symptoms. If a drug ineligible study participant, meaning a household member who does not meet BXM criteria, develops symptoms, they will use an influenza self-test; however, regardless of the result, they will not be able to receive BXM. Nevertheless, the drug ineligible study participant will provide one self-collected or parent/permanent legal guardian-collected nasal swab specimen that will be mailed back to the laboratory for further testing.

If a drug eligible study participant in the household develops a cough or 2 or more respiratory symptoms, he/she will use a prepositioned influenza self-test kit as soon as possible. Additionally, the individual will connect with a healthcare provider through the 98point6 app to

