SFS Statistical Analysis Plan
Household Intervention Study
Last Revised 10/8/19

Applicable to the following UW IRB Study Protocols:

Seattle Flu Study (SFS) **(6181)**

Household Intervention Study **(8200)**

Funding:

Brotman-Baty Institute, University of Washington

Table of Contents

A. STUDY OBJECTIVES AND SUMMARY	3
B. FINAL ANALYSIS PLAN	4
B1. ANALYSIS DATASETS	4
B2. BASELINE TABLES AND STUDY CONDUCT	5
Description of the main tables and statistical analyses	5
Study Accrual	5
Baseline Demographic Characteristics	5
Baseline Behavioral Characteristics	5
Baseline Influenza and Respiratory Illness Symptoms	5
Drug adherence	5
Retention	5
Follow-up	5
B3. SAFETY ANALYSIS	5
B4. ENDPOINT ANALYSIS	5
Primary Analysis	5
Secondary Analyses	5
Additional analyses with Influenza virus infection as the Endpoint	5
Additional analyses with other respiratory infections as Endpoints	5
Sensitivity Analyses	5
C1. INTERIM ANALYSIS PLAN	5
Original plan	5

A. Study Objectives and Summary

Purpose: To evaluate the efficacy of a home-based approach to influenza testing in households in order to shorten the time to diagnosis, antiviral delivery, and antiviral initiation and reduce influenza transmission within the household.

Design: This study is an open cohort intervention study with prospective exposure assessment. It is a pilot study of a home-based approach to influenza infection, utilizing self-test kits and rapid home delivery of baloxavir (BXM). All members of all households must be asymptomatic at enrollment.

Population: Households with at least 3 individuals residing there at least 4 days a week, including at least 2 household members that are eligible to take BXM, will be monitored throughout the influenza season for the onset of a cough.

Expected study size: This study will be conducted in up to 1,000 households in the Seattle, WA area.

Study duration: One influenza season, beginning November 1, 2019 and ending May 1, 2020.

Primary aim: Evaluate whether this home-based strategy leads to a large percentage of influenza-positive individuals initiating antiviral therapy within 48 hours of symptom onset.

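### The SAP's only formal SAE test compares intervention and control periods, and its SAE listing is by shelter; this one-season household cohort has neither a control period nor shelter units.

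*SAP*

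**What the plan says.** SAP B4 (Safety Analysis) plans three things for serious adverse events:

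- a listing: "A list of serious adverse events will be presented by shelter and by treatment v. intervention period";
- a descriptive rate: "The incidence of SAE's (events/person-days of follow-up) will be presented both (1) overall and (2) by case v. non-cases";
- one formal test: "We will test for a difference in SAE rate between the two study periods (intervention v. control) using an exact Poisson test".

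No alpha, sidedness, expected SAE count or power is given for the test. B4 also contains a regression for baloxavir-resistant influenza. It concerns influenza-positive tests, not adverse events, and names no comparison group.

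On design, SAP section A says: "This study is an open cohort intervention study with prospective exposure assessment", and then: "Study duration: One influenza season, beginning November 1, 2019 and ending May 1, 2020". Protocol II says: "This is a pilot study that will evaluate the feasibility of a home-based approach to influenza infection for households in the Seattle, WA area". Protocol V (Weekly Monitoring) starts follow-up on 1 November, or on the day of enrollment for later households.

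For people given the drug, Protocol V (Data collection and Table 1) schedules reaction and AE/SAE questionnaires at 48 hours, 7 days and 14 days. Table 1 marks these only for the drug-eligible group diagnosed with influenza.

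**The concern.** A rate comparison between two periods needs follow-up time in both. If the study has only one period, the one formal SAE comparison in the plan yields nothing, and the listing has no strata to fill. The two descriptions of the strata in B4 also disagree: the listing sets treatment against intervention, which are two words for the same condition, while the test sets intervention against control.

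What would then be left is incidence overall and by case status. SAP section B says its analyses serve DSMB meetings as well as the end of the study. As written, B4 contains no summary defined by receipt of baloxavir and none of non-serious adverse events, although the protocol collects both kinds of event from recipients for 14 days.

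**Working it through.** **1. Is there a control period or a shelter unit anywhere?**

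- Protocol II, IV and V: the enrolled unit is the household. Every enrolled household has at least two drug-eligible members and receives self-tests. Monitoring runs from 1 November or from enrollment. No run-in, crossover or delayed start is described.
- SAP A: open cohort, one season, 1 November 2019 to 1 May 2020 (182 days).
- SAP B5 sizes a two-group cluster-randomized trial, B6 has a Wald test of control against intervention periods, and section C gives influenza rates for two periods. B6 also names a stepped-wedge R package. None of these says who the control is or when.
- Shelter otherwise appears only as a residence-type response in the SAP Table 1a shell.

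**2. What the test does with no control time.** The exact two-sample Poisson test conditions on the total number of events x. Under equal rates,

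X(intervention) | x ~ Binomial(x, π), with π = T(int) / (T(int) + T(ctl)).

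With T(ctl) = 0, π = 1. All x events fall in the intervention period with probability 1, so p = 1. Evaluated at x = 1, 3 and 10, p = 1.0 each time. The control rate is 0/0, so the rate ratio is undefined. The documents give no SAE figure to reproduce.

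**3. Could the periods mean post-dose time against all other time?** SAP section C gives influenza rates of 150 (control), 120 (intervention) and 135 (overall) per 1000. Since (150 + 120)/2 = 135, the SAP's periods carry equal person-time. Post-dose time would not. Assume 14 days per recipient, 63 recipients, 250 households of mean size 3 to 5, and 182 days for every member:

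- post-dose time: 63 × 14 = 882 person-days;
- total, size 3: 250 × 3 × 182 = 136,500, a share of 0.65%;
- total, size 5: 250 × 5 × 182 = 227,500, a share of 0.39%.

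That is far from one half. Nor would such a test be useful. With five SAEs in all, one falling in the post-dose window already gives p = 1 − (1 − 0.00646)^5 = 0.032, although those are also the days of acute illness.

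**4. Does case against non-case stand in for drug exposure?** B4 does not define case. The protocol often uses the word for the person who takes the drug (V, Onset of Symptoms; IX), but its transmission endpoint ties an index case to influenza positivity, and SAP objective S4 refers to cases who are influenza-positive. On the infection reading, the split is not exposure, for three reasons:

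- drug-ineligible participants can have influenza and are never dosed (Protocol II);
- once one member has received baloxavir, no other member of that household can (Protocol II);
- dosing follows a telehealth clinical diagnosis, so a recipient may be laboratory-negative (Protocol II and V).

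**5. What can be estimated.** With zero events in n recipients, the exact two-sided 95% upper limit is 1 − 0.025^(1/n). No document gives an expected number of doses. As an assumption, set n to the expected primary cases in the Protocol II attack-rate table:

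| Household attack rate | n | Upper limit |
|---|---|---|
| 25% | 63 | 5.7% |
| 20% | 50 | 7.1% |
| 10% | 25 | 13.7% |

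**The case against.** The strongest reply is that little is lost. Safety is not among the protocol's primary or secondary endpoints, and Protocol XI plans no SAE test. Recipients are screened three times. Protocol IX sends every SAE to the designated principal investigator for review within 48 hours, with attribution by the medical expert team and onward reporting to the DSMB and IRB. Overall SAE incidence and a plain list can still be produced. All of this stands, and it limits the severity. It does not make the prespecified test possible.

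The SAP also says it applies to two IRB protocols, and the other one is not available here. The period and shelter wording may come from there, but that cannot be settled. The SAP is titled for the household study and its section A describes only that study, so B4 has to work for this design.

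Some stronger readings are tempting but unsupported:

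- *The plan has no other formal analysis under safety.* B4 also holds the resistance regression. The point is confined to SAEs.
- *The case split would charge influenza complications to the drug.* The SAP attaches no ratio or test to that split, and if case means recipient it is close to dosed against undosed. Non-cases are also not simply well people, since they could include symptomatic participants without an influenza diagnosis.
- *The study will give 63 doses.* Sixty-three is the expected number of infections at a 25% household attack rate (Protocol XI). Eligibility, clinical diagnosis and the limit of one recipient per household could make doses fewer or more.

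**Conclusion.** The SAE test and the SAE listing strata in SAP B4 are wrong as written for this study. The test has zero control person-time, an undefined rate ratio and a p-value fixed at 1. This conclusion rests on the design text of both documents and on no numerical assumption.

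The case versus non-case incidence can be produced but needs a definition of case. If case means infection, the split does not describe the safety of the drug.

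The upper limits of 5.7% to 13.7% show what the study could say about SAEs in recipients if none occurred. They depend on the assumed number of recipients and do not measure the defect.

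Severity is moderate. A reader might infer that SAE oversight fails or that SAE reporting is lost. The documents do not support that, because individual review and reporting under Protocol IX does not depend on B4.

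**What to change.** In SAP B4:

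1. Delete the test between periods, and the shelter and period strata in the listing.
2. Report the number and proportion of baloxavir recipients with an SAE, and with any AE, within 14 days of drug receipt, with exact (Clopper-Pearson) 95% confidence intervals. State whether a recipient who did not take the drug stays in the denominator.
3. List SAEs in undosed participants separately, without a test, and note that Protocol Table 1 schedules no AE questionnaire for them, so their events are not ascertained in the same way.
4. If the case versus non-case incidence is kept, define case and its person-days.

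The recipient summaries use data the protocol already collects, so the cost is SAP wording only. Systematic ascertainment of SAEs in undosed participants would be a protocol change and is not needed for this fix. The same period wording in SAP B6 and section C should be reviewed at the same time.
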